6.7.1.11. Hands, Wrists, and Feet Radiographs

Hands, wrists, and feet radiographs will be taken at the time points indicated in the study procedures table (Appendix 2). Note that if a subject discontinues the study early and has had X-rays performed in the <12 week period prior to discontinuation, these do not need to be repeated at ET. Radiographs performed after enrollment may be done +/-7 days of the scheduled visit.

All subjects who discontinue from investigational therapy but continue study visits and procedures, should continue to have radiographs performed as outlined in the study procedure table ([Appendix 2](#)).

The radiographs will be evaluated through central review by independent blinded assessors using the mTSS.

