1.2. Study Design

This is a randomized, double-blind, placebo- and active-controlled, Phase 3 study in adult male and female subjects with active RA who have an inadequate response to MTX (MTX-IR). The study is designed to evaluate the efficacy, safety, and tolerability of filgotinib as well as its effect on work productivity, fatigue, and quality of life.

Approximately 1650 subjects will be randomized in a 3:3:2:3 ratio to filgotinib 200 mg, filgotinib 100 mg, active comparator (adalimumab), or placebo to match (PTM) administered for up to 52 weeks, all in the context of a weekly stable dose of MTX:

- Filgotinib 200 mg group: filgotinib (200 mg q.d.) + PTM filgotinib 100 mg (PTM q.d.) + PTM adalimumab (PTM s.c. injection q2w) (N=450)
- Filgotinib 100 mg group: filgotinib (100 mg q.d.) + PTM filgotinib 200 mg (PTM q.d.) + PTM adalimumab (PTM s.c. injection q2w) (N=450)
- Active comparator group: PTM filgotinib 200 mg (PTM q.d.) + PTM filgotinib 100 mg (PTM q.d.) + adalimumab (40 mg s.c. injection q2w) (N=300)
- Placebo control group: PTM filgotinib 200 mg (PTM q.d.) + PTM filgotinib 100 mg (PTM q.d.) + PTM adalimumab (PTM s.c. injection q2w) (N=450)

Randomization will be stratified by geographic region, prior exposure to biologic disease modifying antirheumatic drugs (bDMARDs), and presence of rheumatoid factor (RF) or anti-CCP (cyclic citrullinated peptide) antibody (Ab) at screening.

At Week 14, subjects who have not achieved at least 20% improvement from Baseline in both swollen joint count (SJC) and tender joint count (TJC) will discontinue investigational study drug dosing but will continue with study visits and assessments per protocol. All subjects meeting this criterion who discontinue from investigational therapy are to receive standard of care treatment for their RA as determined by the investigator.

[figure not shown]
At Week 24, all subjects assigned to placebo + MTX will be reassigned 1:1 to either filgotinib 100 mg q.d. or 200 mg q.d. in addition to MTX in a blinded fashion and will continue in the study per protocol up to Week 52.

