3.8.2. Analysis Visit Windows

Subject visits may not occur on protocol-specified days. Therefore, for the purpose of analysis, observations will be assigned to analysis windows.

In general, the baseline value will be the last nonmissing value on or prior to the first dose date of study drug, except for the mTSS baseline value. The mTSS baseline value will be derived based on the measurements collected on or prior to the first dose date of study drug + 14 days given the potential delay in scheduling an x-ray assessment. If multiple valid, nonmissing measurements exist in the analysis window as aforementioned, in general, the last nonmissing mTSS value on or prior to the first dose date of study drug will be selected as the baseline value; If all these multiple measurements occur at post first dosing, the value closest to the first dose date will be selected as the baseline value.

For subjects who were on placebo and then re-randomized, the baseline after Week 24 will be the last nonmissing value obtained on or prior to the first dose date of filgotinib, except for the mTSS baseline value. The mTSS baseline value will be derived based on the measurements collected on or prior to the first dose date of filgotinib + 14 days given the potential delay in scheduling an x-ray assessment. If multiple valid, nonmissing measurements exist in the analysis window as aforementioned, in general, the last nonmissing mTSS value on or prior to the first dose date of filgotinib will be selected as the baseline value; If all these multiple measurements occur at post first dosing of filgotinib, the value closest to the first dose date of filgotinib will be selected as the baseline value.

For efficacy endpoints, vital signs, ECG, weight, lipids and safety laboratory data, the analysis visit windows will be applied to data collected during the ‘on-treatment’ period. The ‘on-treatment’ period is defined as the last dose date of any study drug + 7 days.

The analysis windows for on-treatment efficacy endpoints including joint count assessment, HAQ-DI (including subject’s pain assessment), subject’s global assessment (SGA), physician’s global assessment (PGA), serum CRP , exploratory patient reported outcome (PRO), and vital signs, weight, and safety laboratory data (lipid data excluded) are provided in [Table 3-1](#) and [Table 3-2](#).

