6. EFFICACY ANALYSES

6.1. General Considerations

The primary analysis set for efficacy analyses will be the FAS, defined in Section 3.1.2.

Efficacy analysis will generally be conducted on the following 2 datasets:

- 1) On-treatment data as specified in Section 3.8.2 with exclusion of the observations described as the following. This is the primary analysis dataset for efficacy analysis.
 - For subjects who continued study drug BUT did not achieve at least 20% improvement from Baseline in both SJC66 and TJC68 at
 - Nominal Week 14 visit, then efficacy data collected after nominal Week 14 visit will be excluded from the primary analysis, OR
 - Nominal Week 12 visit if subjects missed Week 14 visit or the response status cannot be determined due to missing SJC66 or TJC68 value at Week 14, then efficacy data collected after nominal Week 16 visit will be excluded from the primary analysis, OR
 - Nominal Week 16 visit if subjects missed both Week 12 and Week 14 visits or the response status cannot be determined due to missing SJC66 or TJC68 value at both Week 12 and Week 14 visits, then efficacy data collected after nominal Week 16 visit will be excluded from the primary analysis

If subjects missed all three visits (Week 12, Week 14 and Week 16) or the response status cannot be determined at all of these three visits, all the efficacy data collected will be included for analysis

 - Subjects who continued on study drug will be evaluated for loss of therapeutic response from nominal Week 30 visit through nominal Week 52 visit. For subjects who failed to maintain at least a 20% improvement from Baseline in SJC66 and TJC68 (which is confirmed at 2 consecutive visits, and a missed visit will not count against them), efficacy data collected after the second consecutive visit will be excluded from the primary analyses.
- 2) All available data (including data collected under standard of care).

Estimands:

Two efficacy estimands, composite estimand and treatment policy estimand are defined for the primary and key secondary efficacy endpoints, respectively.

The **Composite Estimand** is defined as following. This is the primary estimand for efficacy endpoints.

- 1) Population: Subjects in the FAS.
- 2) Variable: Primary and key secondary endpoints as well as some other secondary endpoints (see details in Section 6.2, 6.3 and 6.4)
- 3) Intercurrent events: The following intercurrent events are taken into account:

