 - If a subject takes standard of care medications due to inadequate response or discontinues from study treatment, treat data as missing from the point of inadequate response or study drug discontinuation (ie, on-treatment data defined above).
 - If a subject discontinues from the study, treat data as missing from the point of loss to follow-up onward.
- 4) Population-level summary: proportion difference for binary efficacy endpoints or mean difference in change from baseline for continuous efficacy endpoints between each filgotinib group and placebo group or adalimumab group if applicable.

The **Treatment-Policy Estimand** is defined as following. This is the secondary estimand for efficacy endpoints.

- 1) Population: Subjects in the FAS.
- 2) Variable: Primary and key secondary endpoints as well as some other secondary endpoints (see details in Section 6.2, 6.3 and 6.4)
- 3) Intercurrent events: The occurrence of an intercurrent event is irrelevant. All observed values will be used regardless of occurrence of an intercurrent event.
 - All observed values will be used regardless of occurrence of an intercurrent event (ie, All available data defined above).
 - If a subject discontinues from the study, treat data as missing from the point of loss to follow-up onward.
- 4) Population-level summary: Proportion difference for binary efficacy endpoint or mean difference in change from baseline for continuous efficacy endpoints between each filgotinib group and placebo group or adalimumab group if applicable.

The other secondary endpoints specified in both estimands include ACR50, ACR70, and the individual components of the ACR response.

To handle the missing data caused by the intercurrent events, the following analyses will be performed for both estimands:

- For binary endpoints, missing data will be treated as non-responder for the primary analysis. Sensitivity analyses including observed data only, last observation carry forward (LOCF), multiple imputation, and tipping point methods will be applied.
- For continuous endpoints, missing data will be handled using a mixed-effects model for the primary analysis. Sensitivity analyses, including using multiple imputation and tipping point methods, will be applied.

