In addition, analyses will be performed for the primary and key secondary endpoints by replacing the population in both estimands with the Per-Protocol analysis set as defined in Section 3.1.3. For these analyses, the binary missing data will be imputed as non-responder and the continuous missing data will be handled using a mixed-effects model.

Selection of Efficacy Data in the Event of Multiple Records in an Analysis Visit Window

If multiple valid, nonmissing efficacy measurements exist in an analysis window, records will be chosen based on the following rules if a single value is needed:

- The record closest to the nominal day for that visit will be selected
- If there are 2 records that are equidistant from the nominal day, or more than 1 record (with time known) on the selected day, the latest record will be taken
- If chronological order cannot be determined (eg, more than 1 record on the same day with time missing), for any given subject, the worst outcome will be selected.

Calculation of Composite Endpoints

For the calculation of composite endpoints including DAS28(CRP), ACR20/50/70, ACR-N, SDAI, and CDAI, we use the following steps unless otherwise specified:

- Step 1: Assign individual components to analysis visit windows defined in Section 3.8.2
- Step 2: Within each analysis visit window, select the component-level data based on the rules for selecting efficacy data as above
- Step 3: Calculate the composite endpoint based on the selected component-level data in Step 2.

Missing Data Imputation

Below are the descriptions for the imputation methods that will be used throughout the efficacy analyses:

- Observed case (OC): Missing values remain missing. For the categorical composite endpoints, in the case that some components are missing, the composite endpoint assessment will be derived based on the non-missing components. If non-missing components are not sufficient to determine final composite endpoint, then the composite endpoint will be set as missing. For continuous composite endpoints (including ACR-N), if any components are missing, the composite endpoints will be set as missing.

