6.4.2. Analysis Methods for Other Secondary Efficacy Endpoints

The FAS will be used for all summaries and analyses of other secondary efficacy endpoints. Statistical testing will be performed up to Week 24. The nominal p-values will be presented, if applicable. No formal statistical testing will be performed after Week 24, unless otherwise specified.

The proportion of subjects who achieve ACR20/50/70, and proportion of subjects with change in HAQ-DI ≥ 0.22 (ie, reduction in HAQ-DI ≥ 0.22), DAS28(CRP) ≤ 3.2 or DAS28(CRP) < 2.6 , will be analyzed using the same logistic regression method with NRI as the primary endpoint analysis described in Section 6.2.3. Comparison will be made between each filgotinib dose group and placebo group. The 2-sided 95% CIs for the proportion based on normal approximation with the sample variance will be provided for each treatment group and visit. In addition, non-stratified response rate difference along with its 95% CI calculated based on the normal approximation with the pooled sample variance will be provided. The OC and LOCF values will be analyzed as a sensitivity approach to the primary method that uses NRI.

The proportion of subjects having no radiographic progression as defined by change from baseline in mTSS ≤ 0.5 at Week 24 will be analyzed using the same logistic regression method based on the OC. Comparison will be made between each filgotinib dose group and placebo group. The 2 sided 95% CIs for the proportion based on normal approximation with the sample variance will be provided for each treatment group. In addition, non-stratified response rate difference along with its 95% CI calculated based on the normal approximation with the pooled sample variance will be provided. The no radiographic progression as defined by change from baseline in mTSS ≤ 0 , and the smallest detectable change (SDC) at Week 24 will also be analyzed using the logistic regression method based on the OC. SDC is the smallest detectable change computed from the variability in change from baseline in mTSS of the two imaging assessors {Bruynesteyn 2005}.

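### No radiographic progression at Week 24 is analysed on observed cases only, so the primary dataset compares subgroups selected by response after randomization; the direction of the resulting bias is unknown

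*SAP*

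**What the plan says.** SAP 6.4.2 uses the FAS for all other secondary endpoints. For no radiographic progression it then says that the proportion with change in mTSS at or below 0.5 "at Week 24 will be analyzed using the same logistic regression method based on the OC", and it treats the cut-offs of 0 and the smallest detectable change likewise. SAP 6.1 defines the method: "Observed case (OC): Missing values remain missing".

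Four further provisions decide which films count as observed.

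- SAP 6.1 says of on-treatment data: "This is the primary analysis dataset for efficacy analysis". Under SAP 3.8.2 the on-treatment "period is defined as the last dose date of any study drug + 7 days".
- Subjects who fail the Week 14 joint-count rule "will discontinue investigational study drug dosing but will continue with study visits and assessments per protocol" (SAP 1.2).
- For those who fail it but stay on drug, SAP 6.1 applies a cut: "Nominal Week 14 visit, then efficacy data collected after nominal Week 14 visit will be excluded from the primary analysis".
- Protocol 6.7.1.11 says that subjects who stop drug but remain in the study "should continue to have radiographs performed as outlined in the study procedure table".

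SAP 6.1 also describes a second dataset of all available data, including data under standard of care, and says that efficacy analysis will *generally* use both. On the estimands it says: "The other secondary endpoints specified in both estimands include ACR50, ACR70, and the individual components of the ACR response". No radiographic progression is not named there.

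**The concern.** Whether a subject enters this analysis depends on joint-count response at Week 14, which treatment is expected to change. The p-value, rate difference and confidence interval then describe subjects who responded well enough to stay on drug in each arm. Randomization does not protect that comparison.

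The treatment of missing data also differs from that of related endpoints. SAP 6.1 sets non-responder imputation as the general primary approach for binary endpoints under both estimands, with observed cases as one of several sensitivity analyses. In SAP 6.4.2, observed cases are likewise only a sensitivity analysis for the ACR, HAQ-DI and DAS28 responses. For no progression they are the only method. Change in mTSS, scored from the same films, is analysed by a repeated-measures model that can use Week 12 films, with multiple imputation and tipping-point analyses in SAP 6.3.3.2.

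At stake is how far the reported share of patients without structural progression reflects the randomized arms.

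**Working it through.** **The plan's own figure.** SAP 1.3 sizes the trial on change in mTSS: difference 0.4, SD 1.85, 90% power, two-sided 0.05. Then n = 2 × (1.960 + 1.282)² × 1.85² / 0.4², which rounds up to 450 per arm; power at 450 is 90.03%. The figure reproduces. The documents give no rate, power or sample size for no progression.

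**Are the films really lost?** Week 14 is nominal Day 99. On-treatment data then end near Day 99 + 7 = Day 106, or Day 109 with the 3-day visit window. The Week 24 mTSS window opens at Day 128 (SAP Tables 3-4 and 3-6). A subject stopped at Week 14 therefore has no Week 24 film in the primary dataset. A Week 12 film is kept but does not enter a Week 24 observed-case analysis.

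There are exceptions. Subjects whose response cannot be determined at Weeks 12, 14 and 16 keep all their data. A film taken on or after Day 128 and within 7 days of a later last dose also counts.

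**Bias formula.** For each arm let q be the share removed, and g the no-progression rate in kept subjects minus that in removed subjects.

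- All-film rate = kept rate − q × g
- Observed-case difference − all-film difference = qF × gF − qP × gP (F filgotinib, P placebo)

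Observed cases understate the difference only if qP × gP exceeds qF × gF.

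**Inputs, all assumed.**

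- Kept rates: 90% filgotinib and 85% placebo, so the observed-case difference is always 5.0 points.
- Largest removal shares: 55% placebo and 35% filgotinib, the complements of the planning ACR20 rates of 45% and 65%. Failing the joint-count rule implies failing ACR20, with Week 12 standing in for Week 14.
- Two smaller pairs: 35%/15% and 20%/10%.

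Bias in percentage points:

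| Gap placebo / filgotinib | Removed 55% / 35% | Removed 35% / 15% | Removed 20% / 10% |
|---|---|---|---|
| 15 / 5 | -6.5 | -4.5 | -2.5 |
| 10 / 10 | -2.0 | -2.0 | -1.0 |
| 0 / 0 | 0 | 0 | 0 |
| 3 / 12 | +2.55 | +0.75 | +0.6 |
| 0 / 10 | +3.5 | +1.5 | +1.0 |

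Top left: 0.35 × 5 − 0.55 × 15 = 1.75 − 8.25 = -6.5. Bottom left: 0.35 × 10 − 0 = +3.5.

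**Where the sign turns.** When more placebo subjects are removed, bias becomes positive once gF/gP exceeds qP/qF: 0.55/0.35 = 1.57, 0.35/0.15 = 2.33, 0.20/0.10 = 2.0.

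**Numbers left.** At 55%/35%, about 202 placebo and 292 filgotinib subjects of 450 each remain.

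**Non-responder imputation is not the remedy.** Counting every removed subject as a progressor at 55%/35% gives 0.65 × 90 − 0.45 × 85 = 58.5 − 38.25 = 20.25 points, which mostly reflects the difference in removal.

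**The case against.** The strongest reply is the second dataset. SAP 6.1 says efficacy analyses will generally use all available data as well, and SAP 3.8.2 applies the same visit windows to data under standard of care. On a natural reading, an observed-case analysis that includes the post-discontinuation films is already intended. This stands in part. But the general wording, together with an estimand list that omits this endpoint, leaves coverage unclear. If run, it would be secondary to the on-treatment result and would still have no imputation for subjects without films.

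A second reply is that on-treatment data are the sponsor's deliberate primary choice. For the other binary endpoints, however, that choice comes with a rule that keeps every FAS subject in the denominator.

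Third, the endpoint is outside the testing hierarchy and its p-values are nominal. Structural benefit is formally tested through change in mTSS, which has its own sensitivity analyses. That is correct and limits the consequence.

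A reader might infer that the analysis understates the treatment effect. That follows if more placebo subjects are removed and the gaps are similar, which is plausible for an effective drug, but the documents do not establish it. Non-responders in every arm receive standard of care between Week 14 and the Week 24 film, which could narrow the placebo gap. Take removal of 15% filgotinib and 35% placebo, with kept/removed rates of 92%/80% on filgotinib. If placebo is 86%/74%, the all-film difference is 90.2 − 81.8 = 8.4 points against 6.0 on observed cases. If placebo is 86%/83%, it is 90.2 − 84.95 = 5.25 points, and observed cases overstate.

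**Conclusion.** The concern holds on selection and on the absent sensitivity analysis. In the primary dataset, the Week 24 no-progression analysis conditions on a post-randomization response and leaves out films that the protocol collects.

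The size is not determined by the documents. The range of about -6.5 to +3.5 points rests wholly on the assumed kept rates, gaps and removal shares, and it measures bias against a target that uses all films regardless of treatment stopping.

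Two further inferences are not supported. One is a specific loss of power: the trial was not powered on this endpoint, and no controlled claim depends on it. The other is that the same argument carries over to Week 52: the Week 52 tests in SAP 6.4.2 compare continuous filgotinib with the placebo-switch groups, and SAP 6.3.3.2 plans mTSS imputation for Week 24 only.

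This is a worthwhile, inexpensive correction to an other secondary endpoint with nominal p-values. It does not threaten the primary or key secondary tests.

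**What to change.** In SAP 6.4.2, for Week 24 and all three cut-offs:

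- Make the main analysis the FAS using all available films, including those taken under standard of care.
- Classify subjects still without a Week 24 film from mTSS data sets imputed by the Week 24 procedure of SAP 6.3.3.2, applied to all available data, and combine the results across imputations. That procedure requires a baseline score, so state how many subjects lack one.
- Keep the on-treatment observed-case analysis as a sensitivity analysis.
- Report, per arm, the number excluded from it and the number classified by imputation.

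The minimum acceptable change is one sentence confirming that the all-available-data analysis covers this endpoint, together with the exclusion counts.

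Cost: SAP wording and one extra derivation; no new films. The downside is that films taken under standard of care enter the main result, so it reflects the assigned strategy including later treatment. SAP 6.1 already accepts this for its treatment-policy estimand.
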